John Hopkins Heart Failure Bridge Clinic (HFBC)

CLINICAL RESEARCH PROTOCOL

Prospective, Randomized, Parallel-Group Pilot Study Comparing IV Furosemide to Subcutaneous Furosemide in Decompensated Heart Failure Patients

Protocol Number: Protocol Date: 2015 - 1 05 August 2015

| | SYNOPSIS |
|----------------------------|---|
| PROTOCOL TITLE | Prospective, Randomized, Parallel-Group Pilot Study Comparing IV Furosemide to Subcutaneous Furosemide in Decompensated Heart Failure Patients |
| PROTOCOL NUMBER | |
| SPONSOR | Johns Hopkins Heart Failure Bridge Clinic (HFBC) |
| INVESTIGATIONAL PRODUCT | Furosemide Injection Solution, (SCP-101) 8 mg/mL manufactured by Cook Pharmica for scPharmaceuticals, Inc. (test treatment) and Furosemide Injection, USP 10 mg/mL (reference treatment) |
| STUDY OBJECTIVES | The objectives of this study are: |
| | Primary objective: To determine the clinical efficacy of subcutaneously administered Furosemide Injection Solution (SCP -101) versus intravenous administration of Furosemide Injection, USP in adult patients at the HFBC presenting with decompensated heart failure. |
| | Secondary objective: To determine the adverse effects and patient satisfaction with subcutaneously administered Furosemide Injection solution (SCP-101) versus intravenous administration of furosemide in adult patients at the HFBC presenting with decompensated heart failure. |
| STUDY DESIGN & DURATION | This clinical trial is a prospective, randomized, parallel-group pilot study comparing the intravenous administration of Furosemide Injection, USP, to subcutaneous administration of a buffered furosemide formulation - Furosemide Injection Solution (SCP-101), in patients presenting to the Johns Hopkins Hospital Heart Failure Bridge Clinic (HFBC) with decompensated heart failure. Patients presenting to the HFBC will be assessed to determine whether they need IV diuretics. If they do, they will be screened for eligibility. If they are eligible, written informed consent will be obtained. Patients will then be randomized to receive Furosemide Injection, USP intravenously or Furosemide Injection Solution (SCP-101) delivered subcutaneously. The IV patients will get the usual care of the HFBC, which includes having an IV placed and delivery of a one-time dose of IV furosemide with the dose determined by the providers (maximum dose 160mg IV). The subcutaneous patients will receive 80mg of Furosemide Injection Solution (SCP-101) administered subcutaneously over 5 hours (30mg in first hour and 12.5mg/hour for 4 hours). Administration will take place with the B Braun Perfusor® Space Infusion Pump System and a standard commercial infusion set. Both groups of patients will be observed for 6 hours to assess diresis. The goal will be to enroll a total of 40 patients, 20 in the IV furosemide group, and another 20 in the subcutaneous furosemide group. Vital signs and urine output will be monitored closely for 6 hours. Patients will be asked to fill out a survey about their symptom improvement (Kansas City Cardiomyopathy questionnaire) and overall satisfaction related to the treatment experience. They will also be monitored for side effects including ototoxicity and discomfort at the access site (burning, itching, and pain). Electrolytes and renal function will be checked once after the patients receive diuretic therapy. Study participants will be on fluid |

| | restriction during the study, with no more than 100ml of fluid consumed during the 6 hours. |
|----------------------------|--|
| | Study Drug: |
| | Furosemide Injection, USP: Furosemide Injection, Solution, single dose determined by Investigator (maximum dose 160mg) administered intravenously by IV bolus over approximately 2 minutes (reference treatment) |
| | • Furosemide Injection Solution (SCP-101), 8 mg/mL: 80 mg dose administered subcutaneously as 30 mg over the first hour and then as 12.5 mg per hour over the subsequent 4 hours (test treatment) |
| | Since the HFBC gives IV diuretics about 15 times per month, HFBC plans to enroll 40 patients within three to four months. The study requires only one clinical visit – a visit that would have already been scheduled for the patient. |
| NUMBER OF SUBJECTS | The number of subjects in this prospective study is 40. 20 in the IV furosemide group and another 20 in the subcutaneous furosemide group. |
| NUMBER OF SITES | 1 |
| PARTICIPATING COUNTRIES | US |
| SUBJECT POPULATION | Female and male subjects may be enrolled in the study only if all of the inclusion criteria and none of the exclusion criteria are met. |
| | Inclusion Criteria (low risk, intermediate risk): |
| | An Institutional Review Board (IRB) approved informed consent is signed and dated prior to any study-related activities. Male and female subjects ≥ 18 years of age History of at least 3 months treated heart failure (NYHA class II/III/IV), or recent hospitalization for heart failure; presenting to HFBC with decompensated heart failure symptoms including elevated jugular venous pressure, dyspnea and peripheral edema where the decision is made to give IV diuretics Able to participate in the study in the opinion of the investigator Has the ability to understand the requirements of the study and is willing to comply with all study procedures |
| | Exclusion Criteria (high risk): |
| | A subject is not eligible for inclusion if any of the following criteria apply: |
| | • Presenting with symptoms where it is anticipated that there is a high chance of hospitalization such as ischemia, uncontrolled arrhythmia, infection, hemodynamic instability (elevated or low blood pressure), respiratory compromise, or electrolyte |

| | abnormalities (>25% increase in creatinine from baseline, |
|-------------------------|---|
| | potassium, hyponatremia). |
| | • On experimental medication or currently participating in a |
| | cardiovascular research study. |
| | • Presence or need for urinary catheterization, urinary tract |
| | abnormality or disorder interfering with urination |
| | • Any surgical or medical condition which in the opinion of the investigator may interfere with participation in the study or which may affect the outcome of the study |
| | Inability to comply with study requirements |
| ENDPOINTS | Primary Endpoints: |
| | Total volume of voids over a 6-hour period Total natriuresis over a 6-hour period |
| | Secondary endpoints: |
| | Volume of voids between 0-2 hours, 2-4 hours and 4-6 hours post initiation of treatment. Heart Failure Symptom Scoring/Symptom Improvement- (Kansas City Cardiomyopathy questionnaire) Overall Satisfaction with Treatment- (Treatment Satisfaction |
| | Survey) |
| | Safety endpoints: |
| | Patient reported Pain Increases in serum creatinine of 0.5 mg/dL or greater Local skin reactions including hematoma, induration, infection, thrombosis, necrosis etc. Occurrence of treatment-emergent Adverse Events (AEs) or Serious Adverse Events (SAEs) |
| STATISTICAL ANALYSIS | Determination of Sample Size: For this pilot study, the determination of sample size was primarily based on clinical consideration; with the aim to yield meaningful preliminary data. |
| | Statistical Analysis Plan: A full statistical analysis plan will be developed. All data will be analyzed as intention-to-treat. Continuous variables will be presented as mean \pm standard deviation and will be compared using the Students t -test (2-tailed), unpaired. Differences between treatment groups for the categorical variables will be analyzed using the chi-square test. For the purposes of this study, P values \leq .05 will be considered significant. |
| | Early Stopping Rules: The study will be stopped early if there is a significant difference in number of patients with intolerable side effects: Ototoxicity, severe discomfort, burning and stinging at the access site, itching, and/or pain. |

| Time and Events Table | Screening Phase | Pre-Dose | Start of Dosing | Dosing | 6 hours post Start of Dosing |
|---|--------------------|----------|--------------------|--------|---------------------------------|
| Informed Consent | Х | | | | |
| Confirmation of Eligibility | Х | | | | |
| Co-morbidity | Х | | | | |
| Cardio-Pulmonary Examination | Х | | | | |
| Serum Creatinine | Х | | | | Х |
| Weight and Height | Х | | | | |
| Vital Signs | Х | Х | Х | Х | Х |
| 12-lead EKG | Х | | | | |
| Collection and Measurement of Urine Voids | | | Х | Х | Х |
| Urine Sodium | | Х | | | Х |
| Clinical Chemistry | Х | | | | Х |
| BNP/NT ProBNP | | Х | | | Х |
| Study Drug Administration | | | Х | | Х |
| Injection Site Pain Assessment | | | | | Х |
| Injection Site Inspection | | Х | | | Х |

1. INTRODUCTION

The prevalence of chronic heart failure is increasing, and it is the most common diagnosis in hospital patients age 65 years and older. Despite advances in the treatment of chronic heart failure, in-hospital mortality and readmission are high. Heart failure costs the US about 32 billion per year, and a large percentage of the costs are due to hospitalizations. The Heart Failure Society of America guidelines for the management of decompensated heart failure offer recommendations for clinical circumstances that should prompt hospital admission. Most clinicians would agree that patients with decompensated heart failure presenting with hypotension, worsening renal function and altered mental status should be hospitalized. However, there is a subset of patients presenting with dyspnea and edema due to volume overload that necessitate rapid symptom improvement but are hemodynamically stable. Oral diuretics would likely be ineffective but admission for IV diuretics seems excessive.

The Johns Hopkins Heart Failure Bridge Clinic (HFBC) was designed as a clinic to reduce heart failure hospital admissions. Patients with chronic heart failure are primarily seen either in the early post discharge period or if they are referred for an infusion of IV diuretic. The HFBC sees about 160 patients each month and administers on average 15 infusions of Intravenous (IV) diuretics. The average visit duration is 220 minutes, with mean IV furosemide dose 100mg resulting in average urine output 1460 ± 730 ml, and weight loss of 2.3 ± 1.8 kg.

The HFBC has been successful at preventing hospital admissions by treating patients with IV diuretics. However, it requires patients to come to the clinic for treatment and close monitoring. Subcutaneous diuretics present a potential alternative to IV diuretics and offer patients an opportunity to receive treatment outside of the hospital setting. Very few studies have evaluated the efficacy and safety of subcutaneous furosemide in chronic heart failure patients presenting with symptoms of volume overload.

1.1. Rationale for the Current Study

The research hypothesis is that subcutaneously administered furosemide will be an effective alternative to IV furosemide for hemodynamically stable chronic heart failure patients presenting with volume overload in the ambulatory setting. The significance of this research is finding a potential intervention that could help decrease heart failure hospitalizations and improve the quality of life for patients with chronic heart failure. In addition, we can decrease the costs associated with heart failure.

There is very little experience with subcutaneous administration of furosemide EP/USP (current form of commercially available furosemide injection solution). There are a few studies that show the delivery of subcutaneous furosemide by electric infusion pump in terminally ill patients is effective for weight loss and symptom improvement (1,2). A group in Spain was successfully able to resolve 41 episodes of decompensated heart failure in 24 elderly patients using continuous subcutaneous furosemide administered by elastomeric infusion pumps (2). They found that the elastomeric infusion pumps provided safe outpatient treatment without the need for daily monitoring. In addition, it helped prevent hospital admissions and decreased costs due to the low price of the devices. It was also a good alternative for patients with venipuncture failure and the inability to transition from intravenous to oral diuretics.

Furosemide USP has a pH of 8.3 -9.0 and may cause irritation and discomfort upon administration. A novel buffered formulation with a physiologic pH (7.4) is currently under development in support of a NDA submission later in 2015. The product is to be marketed with a wearable patch pump for a slow 5-hour administration to optimize 8-hour diuresis.

scPharmaceuticals, Inc. (Lexington, MA), the developer of the novel furosemide formulation and its drug delivery device, provided the following information. The pivotal clinical study with the buffered furosemide solution (Furosemide Injection Solution (SCP-101)) started in Q2 of 2015 in support of the NDA. This study is conducted in the United States in stable HF patients under IND 118,919.

The company has previously conducted a Phase I pilot study (NCT02350725) to investigate the pharmacodynamics and pharmacokinetic parameters of Furosemide Injection Solution (SCP-101) administered subcutaneously as compared to oral furosemide. The study was a randomized open-label cross-over study in patients with stable HF. Patients were mildly symptomatic with NT-proBNP of >300 pg/mL. Treatments were separated by a 14 +/- 3 day interval. Subcutaneous administration of Furosemide Injection Solution (SCP-101) (8mg/mL; 80 mg total), was delivered using a B Braun Perfusor® Space Infusion Pump System as 30 mg over the first hour followed by 12.5 mg per hour over the subsequent 4 hours. Reference treatment consisted of 80mg p.o. furosemide.

Ten subjects were enrolled (80% males) with a mean age of 69.9 years and mean plasma NTproBNP of 1638 ng/mL. All patients were on standard medication including ACE inhibitors and beta blockers. Main daily dose of oral furosemide was 40 mg/day.

Subcutaneous administration of the novel formulation was well-tolerated. All participants achieved therapeutic plasma furosemide levels of over 1000ng/mL within one hour of start of subcutaneous infusion. Therapeutic plasma levels were maintained for a minimum of 5 hours (Figure 1).

Figure 1: Mean Plasma Furosemide Levels after SC or Oral Administration

Figure 1. Plasma furosemide levels were measured just prior to dosing (Time 0) and at 30, 60, 120, 240, 300, 360 and 480 minutes post dosing. Mean plasma levels + 2 SE across the 10 subjects are shown for each treatment period.

Plasma furosemide levels in the plateau phase (60-300 minutes post start of infusion) were maintained in a narrow range (67%-93%) from the Cmax when compared to oral (11% - 40%). P.o. furosemide administration resulted in highly variable plasma levels: 90% of the participants achieved levels of 1000ng/mL at some point following administration; but only one participant (10%) maintained plasma levels over 1000 ng/mL for 5 hours. The mean total furosemide exposure (expressed by area under the curve, AUC) was 66% higher after subcutaneous administration when compared to oral (p < 0.0001).

2. STUDY OBJECTIVES

The objectives of this study are:

(1) Primary objective: To determine the clinical efficacy of subcutaneously administered Furosemide Injection Solution (SCP-101) versus intravenous administration of Furosemide Injection, USP in adult patients at the HFBC presenting with decompensated heart failure.

(2) Secondary objective: To determine the adverse effects and patient satisfaction with subcutaneously administered SCP-101 versus intravenous furosemide in adult patients at the HFBC presenting with decompensated heart failure.

3. INVESTIGATIONAL PLAN

3.1. Overall Study Design and Plan

This clinical trial is a prospective, randomized, parallel-group pilot study comparing the intravenous administration of Furosemide Injection, USP, to subcutaneous administration of a buffered furosemide formulation – Furosemide Injection Solution (SCP-101), in patients presenting to the Johns Hopkins Hospital Heart Failure Bridge Clinic with decompensated heart failure. Patients presenting to the HFBC will be assessed to determine whether they need IV diuretics. If they need it, they will be screened for eligibility. If they are eligible, written informed consent will be provided. Patients will then be randomized to receive Furosemide Injection, USP intravenously, or SCP-101 delivered subcutaneously. The IV patients will get the usual care of the Heart Failure Bridge Clinic, which includes having an IV placed and delivery of a one-time dose of IV furosemide with the dose determined by the providers (maximum dose 160mg IV). The subcutaneous patients will receive 80mg of Furosemide Injection Solution, 8 mg/mL, administered subcutaneously over 5 hours (30mg in first hour and 12.5mg/hour for 4 hours).

Administration will take place with the BBraun Perfusor® Space Infusion Pump System and a standard commercial infusion set. Both groups of patients will be observed for 6 hours to assess diuresis. The goal will be to enroll a total of 40 patients, 20 in the IV furosemide group, and another 20 in the subcutaneous furosemide group. Vital signs and urine output

will be monitored closely for 6 hours. Patients will be asked to fill out a survey about their symptom improvement (Kansas City Cardiomyopathy questionnaire) and overall satisfaction related to the treatment experience. They will also be monitored for side effects including ototoxicity and discomfort at the access site (burning, itching, and pain). Electrolytes and renal function will be checked once after the patients receive diuretic therapy. Study participants will be on fluid restriction during the study, with no more than 100 ml of fluid consumed during the 6 hours.

Study Drug:

- *Furosemide Injection, USP:* Furosemide Injection, Solution, single dose determined by Investigator (maximum dose 160mg) administered intravenously by IV bolus over approximately 2 minutes (reference treatment).
- *Furosemide Injection Solution, 8 mg/mL (SCP-101):* 80 mg dose administered subcutaneously as 30 mg over the first hour and then as 12.5 mg per hour over the subsequent 4 hours (test treatment)

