4.4. Removal of Subjects from Therapy/Premature Discontinuation

Participants may discontinue participation at any time without penalty or loss of benefits to which the subject is otherwise entitled.

The subject's participation may be terminated by the investigator for safety reasons or if, in the opinion of the investigator, continued participation may interfere with clinical management.

The study will be stopped early if there is a significant difference in number of patients with intolerable side effects: Ototoxicity, severe discomfort, burning and stinging at the access site, itching, and/or pain.

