7.4. Assessment of Relatedness to Study Drug

The Investigator will assess each AE and SAE for causality based on their medical judgment and the observed symptoms associated with the event. Each AE and SAE will be assessed as related or unrelated to study drug based on the following criteria:

- Unrelated This category applies to those AEs that the Investigator determines are most likely due to extraneous causes (disease, environment, etc.)
- Related This category applies to those AEs that the Investigator determines are most likely due to test drug.

7.5. Method, Frequency, and Time Period for Detecting Adverse Events and Serious Adverse Events

Patients will be evaluated for AEs and SAEs at the end of the 6 hour observation. After the subject has had an opportunity to spontaneously mention any problems, the Investigator should inquire about AEs by asking a non-leading question such as "How are you feeling?"

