Appendix 1: Time and Events Schedule

| Time and Events Table | Screening Phase | Pre-Dose | Start of Dosing | Dosing | 6 hours post Start of Dosing |
|---|--------------------|----------|--------------------|--------|---------------------------------|
| Informed Consent | Х | | | | |
| Confirmation of Eligibility | Х | | | | |
| Co-morbidity | Х | | | | |
| Cardio-Pulmonary Examination | Х | | | | |
| Serum Creatinine | Х | | | | Х |
| Weight and Height | Х | | | | |
| Vital Signs | Х | Х | Х | Х | Х |
| 12-lead EKG | Х | | | | |
| Collection and Measurement of Urine Voids | | | Х | Х | Х |
| Urine Sodium | | Х | | | Х |
| Clinical Chemistry | Х | | | | Х |
| BNP/NT ProBNP | | Х | | | Х |
| Study Drug Administration | | | Х | | Х |
| Injection Site Pain Assessment | | | | | Х |
| Injection Site Inspection | | Х | | | Х |
| Randomization to Treatment Sequence | Х | | | | |
| Kansas City Cardiomyopathy questionnaire | | Х | | | Х |
| Treatment Satisfaction Survey | | | | | Х |
| Treatment Emergent Serious Adverse Events | | | X | X | Х |

Verbally indicate the number on the Numeric Rating Scale that best represents the intensity of pain at or around the injection site NOW, with 0 being no pain and 10 being the worst possible pain.

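### Ototoxicity, burning and itching are monitored effects and grounds for stopping the study, but no instrument, baseline or scheduled time point specifically captures them

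*Combined protocol and SAP*

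**What the plan says.** **Commitment.** The Synopsis and section 3.1 both promise monitoring: "They will also be monitored for side effects including ototoxicity and discomfort at the access site (burning, itching, and pain"). Adverse effects are part of the secondary objective (section 2).

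**Stopping rule.** The Synopsis and section 4.4 stop the study on a significant between-group difference in the number of patients with "intolerable side effects: Ototoxicity, severe discomfort, burning and stinging at the access site, itching, and/or pain". Neither place gives a look time, a test or a definition of intolerable.

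**Schedule.** Table 1 in the Synopsis and Appendix 1 carry the same rows. The relevant ones are:
- "Injection Site Pain Assessment": 6 hours only.
- "Injection Site Inspection": pre-dose and 6 hours.
- "Treatment Emergent Serious Adverse Events": start of dosing, during dosing and 6 hours.

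**Rating scale.** Section 6.1.8 describes a 0-10 verbal rating, given once at the end of observation, that covers discomfort of any kind. The card, printed after the schedule in Appendix 1, asks instead for "the intensity of pain at or around the injection site NOW".

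**Adverse events.** Section 7.5 says: "Patients will be evaluated for AEs and SAEs at the end of the 6 hour observation". The patient may first raise problems unprompted, and the investigator then asks a non-leading question. The opening of section 7 says that assessment is continuous from dosing to discharge, but names no method.

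**The concern.** A site that follows the schedule to the letter has no prompt to ask about hearing, ringing, burning or itching, and no form on which the answer must appear. Ototoxicity, the first effect in the stopping rule, is also not named in the safety endpoints (3.1.2), the safety assessments (6.1.2) or the safety analyses (8.3).

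Two things are at stake. The report could describe an effect as absent when it was never specifically asked about. And the stopping rule compares counts of patients between arms, so it is only as good as those counts. In a trial of this size the comparison turns on very few patients.

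**Working it through.** The plan gives no figure to reproduce: section 8.1 bases the sample size on clinical consideration, and the stopping rule has no number. The check has two parts.

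**1. Each named effect against each means of capture**

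| Effect | Own row in either schedule | Pre-dose status | What could record it |
|---|---|---|---|
| Ototoxicity | None | No specific item | Unprompted mention, open question at 6 hours, unspecified continuous assessment |
| Burning or stinging | None | None | As above, plus the 0-10 rating if read as in 6.1.8 |
| Itching | None | None | As above, plus the 0-10 rating if read as in 6.1.8 |
| Pain | Yes, 6 hours only | None | The 0-10 rating |

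The site inspection (6.1.9, Appendix 3) scores erythema and edema on the Draize scale. It then lists other local reactions such as hematoma and induration. These are signs that staff observe, not sensations that the patient reports.

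**Timing of the rating.** The subcutaneous infusion lasts 5 hours, so a rating at 6 hours comes 6 - 5 = 1 hour after it ends. The IV bolus lasts about 2 minutes, so the rating comes about 5 hours 58 minutes after it. A card that asks about the present moment can therefore return 0 for a symptom that was present during dosing and has since gone.

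**2. How few patients decide the comparison**

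Inputs: 20 patients per arm (section 3.1); chi-square test for categorical variables and P ≤ .05 (section 8.2). The stopping rule names no test, so the section 8.2 test is assumed. Fisher's exact test is shown beside it because the expected event counts are small: with 4 events in all, 4 × 20/40 = 2 per arm.

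For *a* and *b* patients with events out of *n* per arm, N = 2n:

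χ² = N × [a(n - b) - b(n - a)]² / [n × n × (a + b) × (N - a - b)]

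- 0 vs 3: 40 × 60² / (20 × 20 × 3 × 37) = 144,000/44,400 = 3.24, P = 0.072.
- 0 vs 4: 40 × 80² / (20 × 20 × 4 × 36) = 256,000/57,600 = 4.44, P = 0.035.

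Fisher, two-sided, with no events in one arm: P = 2 × C(20, b)/C(40, b).

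- 0 vs 4: 2 × 4,845/91,390 = 0.106.
- 0 vs 5: 2 × 15,504/658,008 = 0.047.

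Chi-square with continuity correction first reaches P ≤ .05 at 0 vs 6: 40 × (120 - 20)² / (20 × 20 × 6 × 34) = 400,000/81,600 = 4.90, P = 0.027.

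With one event in the other arm, the smallest significant splits are 1 vs 6 (uncorrected, P = 0.037) and 1 vs 7 (Fisher, P = 0.044).

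So under the uncorrected test, one unrecorded patient turns 0 vs 4 (P = 0.035) into 0 vs 3 (P = 0.072).

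An early stop would be decided on fewer than 40 patients. If a look took place at 10 per arm (an assumption), 0 vs 4 gives 20 × 40² / (10 × 10 × 4 × 16) = 32,000/6,400 = 5.00, P = 0.025. 0 vs 3 gives 20 × 30² / (10 × 10 × 3 × 17) = 18,000/5,100 = 3.53, P = 0.060. The threshold is again four patients.

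**The case against.** The strongest reply is that the plan captures more than the schedule shows.

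- **Discomfort is rated.** Section 3.1 spells out access-site discomfort as burning, itching and pain, and section 6.1.8 asks for a rating of any discomfort. On that reading the 6-hour scale covers all three. This stands in part: burning and itching are not wholly unmeasured. But one number cannot separate them, there is no baseline, and the card's wording is narrower than the section's.
- **The investigator asks.** A reader might infer that the whole stopping rule runs on what patients volunteer. The documents do not support that. Pain has a scheduled scale, section 7.5 requires an open question, section 7 describes continuous assessment, and section 7.6.4 requires all adverse events to be documented. What remains is that none of these names hearing, burning or itching.
- **Baseline exists in outline.** Co-morbidity is recorded at screening, and section 7.1 does not count a pre-existing condition that does not worsen. Applying that rule to a hearing complaint still requires that the prior state was asked about. Randomization balances prior complaints only in expectation and does not show whether a given patient's complaint is new.
- **Unseen forms may help.** The items of the Treatment Satisfaction Survey and the CRF are not in the documents, so they may touch on these symptoms. The survey is scheduled only at 6 hours, and nothing links it to section 4.4.
- **Open questions are a legitimate choice.** Prompting raises reports of minor symptoms. In an open-label trial it may do so unequally between routes. This stands as a cost of the fix.

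A reader might also infer from the contrast between a 2-minute bolus and a 5-hour infusion that hearing effects should differ between arms. The documents draw no such link, and the point does not depend on it.

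**Conclusion.** The concern holds in a limited form. Three effects are promised as monitored and used as grounds for stopping, but none has its own instrument, baseline or scheduled time point. Ototoxicity depends on general adverse-event reporting. Burning and itching depend on a single rating whose two descriptions disagree.

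The size is best put as the number of patients that decides the comparison: four to six in one arm with none in the other, depending on the test. This assumes that the rule uses the section 8.2 significance level and that the arms are equal in size. How likely an event is to be missed cannot be estimated, because the documents give neither event rates nor capture rates.

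This is an inexpensive improvement to safety ascertainment. It does not affect the primary endpoints.

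**What to change.** 1. Add a *Directed symptom check* row to Table 1 and Appendix 1, at pre-dose and 6 hours, in both arms. At 6 hours ask it after the open question, so that unprompted reports are kept. Use fixed items on (a) hearing loss or ringing, new or worse at 6 hours, (b) burning or stinging at the access site, and (c) itching at the access site. The 6-hour items should cover any time since the start of dosing. Record for each its severity and whether the patient found it tolerable.
2. Reconcile section 6.1.8 with the card, so that the rating covers discomfort since the start of dosing.
3. Extend the adverse-event row in both schedules from serious events to all adverse events.
4. State in section 4.4 that its counts draw on this form together with reported adverse events.

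The cost is about one CRF page, with no extra staff. The downside is more reports of minor symptoms, possibly unequal between arms because the trial is open label; keeping prompted and unprompted reports apart lets the reader see this. The form supplies the counts but does not by itself make the stopping rule workable: its look times, its test and the meaning of intolerable remain for the trial team to define.
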